7.4 Reporting Adverse Events

7.4.1 *Reporting serious adverse events*

Sponsor-Institution and Sponsor-Investigator shall be responsible for reporting any and all serious adverse events associated with the use of the Study Drug to the FDA via MedWatch (FDA Form 3500A), with a copy to Astellas via e-mail to [contact], or fax to [contact] and, when necessary, to the applicable IRB.

Life-threatening (grade 4 or 5) SAEs, events determined to be medically significant by the treating Investigator, and unknown reactions or unexpected events should be reported to the principal investigator, site IRB and the lead site/sponsor within 24 hours and be reported according to institutional and the following guidelines.

SAEs that are fatal and possibly protocol related and any treatment emergent seizure events should be reported by phone to the Protocol Chair immediately upon knowledge of the event.

The Lead Center's Study Coordinator should be contacted when reporting an SAE or death. If this person cannot be reached within 24 hours, the Protocol Chair (Lead Center's PI) should be contacted: [name], [contact].

The initial report for each SAE or death should include the following information:

- Protocol # and title
- Patient initials, study identification number, age
- Date the event occurred
- Description of the SAE
- Dose level and treatment month at the time the SAE occurred
- Description of the patient's condition
- Relationship of SAE to study drug/treatment (see Table 6)
- Indication whether the patient remains on study

Follow-up information including severity, causality, action taken, concomitant medications, and outcome should be communicated to the lead site/sponsor as soon as possible with an indication whether an amendment will need to be made to the protocol, the consent form, or both, as a result of this event.

7.4.2 *Reporting SAEs at multi-site/participating institutions*

A subject's AEs and SAEs will be recorded and reported from the signing of the ICF up to at least 30 days after completing salvage radiotherapy. The investigator must instruct the subject to report AEs and SAEs during this time period.

Subjects with evidence of enzalutamide related toxicity at the post-treatment follow-up visit will be followed via telephone contact or weekly visits until the drug-related toxicity has resolved. Adverse events should be based on the signs or symptoms detected during the physical examination and on clinical evaluation of the subject. In addition to the information obtained from those sources, the subject should be asked the following nonspecific question: "How have you been feeling since your last visit?" Signs and symptoms should be recorded using standard medical terminology. Any unanticipated risks to the subjects must be reported promptly to the IRB/IEC. In the event of an adverse event the first concern will be for the safety of the subject.

All AEs and SAEs must be recorded on source documents. All AEs and SAEs for subjects who meet inclusion and exclusion criteria will be recorded in the CRFs and submitted to the lead site. The investigator must follow up on all AEs and SAEs until the events have subsided, returned to baseline or, in case of permanent impairment, until the condition stabilizes.

Additional reporting is required for SAEs as follows:

- SAEs that are fatal and possibly protocol related should be reported by phone to the Protocol Chair immediately upon knowledge of the event.

Each participating site is responsible for evaluating and completing any additional reporting to their local IRB according to local IRB guidelines.

8. CRITERIA FOR OUTCOME ASSESSMENT

8.1 Outcome Assessment

All baseline evaluations will be performed as closely as possible to the beginning of treatment. For subsequent evaluations, the method of assessment and techniques will be the same as those used at baseline.

- Measurement of clinical lesions
- Chest x-ray

Should be conducted at PSA progression. Scans can also be obtained sooner as clinically indicated.

- Conventional CT, MRI

Should be conducted at PSA progression. Scans can also be obtained sooner as clinically indicated.

- Ultrasound

- Endoscopy/laparoscopy

- Tumor markers

FFPP is defined as the time from randomization to the date of PSA progression. A subject who does not have PSA progression at the time of the analysis will be censored at the last date of PSA measurement. In patients who achieve an

undetectable PSA value (defined as ≤ 0.1 ng/mL), PSA progression is defined as a detectable PSA value (≥ 0.2 ng/mL) that is confirmed by a second consecutive PSA value obtained ≥ 8 weeks later which is higher (and ≥ 0.4 ng/mL). In patients who do not achieve an undetectable PSA, PSA progression is defined as a 0.2 ng/mL increase from nadir that is confirmed by a second consecutive PSA value obtained ≥ 8 weeks later which is higher.

- Cytology/histology

8.1.1 *Primary endpoint*

The primary objective of the study is to evaluate the efficacy of the two treatment regimens based on freedom-from-PSA-progression (FFPP). Overall survival has been the preferred primary endpoint for most phase III trials in metastatic prostate cancer, as well as for most registration trials for other metastatic malignancies. Many of the practice-changing adjuvant trials, however, have used disease-free or progression-free survival as the primary endpoint^{38,39}. Probably the most analogous adjuvant therapy is the use of endocrine therapy for early stage breast cancer. The primary endpoint for many of the trials evaluating tamoxifen and the aromatase inhibitors has been disease-free survival⁴⁰⁻⁴³. Several of the described prostate cancer adjuvant trials reported a lower-than-expected event rate requiring re-assessment of sample size and follow-up time. Even men with the highest risk prostate cancers are likely to survive beyond 12 years after prostatectomy⁴⁴. This data originated in the pre-docetaxel era and does not reflect the arsenal of new therapeutic agents that have become available to patients with advanced prostate cancer. We do not yet have reported data for survival after prostatectomy that accounts for these new treatments, which makes estimating survival a challenge. Furthermore, cabazitaxel, abiraterone acetate, enzalutamide, and alpharadin were all tested in advanced metastatic disease patient populations, so although we know the benefits of these drugs individually, the impact on survival when administered sequentially has not been established. We estimate that with the approval of cabazitaxel, sipuleucel-T, abiraterone acetate, enzalutamide, and radium-223, men may live as long as 15-20 years after prostatectomy. The size, duration, and cost of a trial powered to detect an overall survival benefit in this setting for prostate cancer is substantial and such trials must be carefully designed to ensure responsible utilization of resources. Despite these challenges, it is important to move novel therapies earlier in the treatment of prostate cancer with the hope that these agents improve cure rates such that the long-term cost-benefit ratio is favorable. The ultimate goal of adjuvant systemic therapy is to increase the number of patients cured of their cancer. The earliest indication of prostate cancer relapse is a rising PSA after definitive local therapy. For these reasons, we will use 2-year FFPP defined as our primary endpoint. FFPP reflects a clinically meaningful endpoint for high-risk patients, yet minimizes the patients and resources necessary to answer this question.

FFPP is defined as the time from randomization to the date of PSA progression. A subject who does not have PSA progression at the time of the analysis will be censored at the last date of PSA measurement. In patients who achieve an undetectable PSA value (defined as ≤ 0.1 ng/mL), PSA progression is defined as a detectable PSA value (≥ 0.2 ng/mL) that is confirmed by a second consecutive PSA

value obtained ≥ 8 weeks later which is higher (and ≥ 0.4 ng/mL). In patients who do not achieve an undetectable PSA, PSA progression is defined as a 0.2 ng/mL increase from nadir that is confirmed by a second consecutive PSA value obtained ≥ 8 weeks later which is higher.

8.1.2 Secondary endpoints

The first secondary endpoint is time to local recurrence within the radiation field, defined as the time from randomization to the date of local recurrence of disease. Subjects who do not have local recurrence will be censored on the date of their last evaluable tumor assessment for local recurrence. Subjects who start any subsequent anti-cancer therapy without a prior reported local recurrence will be censored at the last evaluable tumor assessment prior to initiation of the subsequent anti-cancer therapy.

The second secondary endpoint is radiographic metastasis free survival (rMFS), defined as the time from randomization to the date of metastasis or death from any cause, whichever occurs first. A subject who does not have metastasis and is alive will be censored at the last date of tumor assessment. We will pay particular attention to the 2-year MFS rate.

Safety and tolerability will also be evaluated as secondary objectives.

9. DATA REPORTING AND REGULATORY REQUIREMENTS

The SKCCC Lead Coordinating Center will monitor the conduct and progress of the clinical trial at all participating sites. It will provide administrative, data management, regulatory, and organizational support in the conduct of this multi-center trial. The Coordinating Center will also function as the central location for multi-center trial documents and patient registration. For more information regarding reporting, regulatory requirements and guidelines, see Appendix D.

9.1 *Multicenter Guidelines*

9.1.1. *The Protocol Chair*

The Protocol Chair, [name], is responsible for performing the following tasks:

- Taking responsibility for the overall conduct of the study at all participating institutions and for monitoring the progress of the study.
- Coordinating, developing, submitting, and obtaining approval for the protocol as well as its subsequent amendments.
- Assuring that all participating institutions are using the correct version of the protocol.
- Reviewing and ensuring reporting of Serious Adverse Events (SAEs).
- Reviewing data from all sites

9.1.2. *Lead Coordinating Center*

The Lead Center SKCCC, Johns Hopkins University is responsible for performing the following tasks:

- Verifying that each participating institution has a Federal Wide Assurance (FWA) number.
- Ensuring that IRB approval has been obtained at each participating site prior to the first patient registration at that site.
- Maintaining copies of IRB approvals from each site.
- Implementing central patient registration
- Prepare appropriate data as required for review by the Protocol Chair.
- Establishing procedures for documentation, reporting and submitting of AE's and SAE's to the Protocol Chair and all other applicable parties.
- Facilitating audits by securing selected source documents and research records from participating sites for audit, or by auditing at participating sites.

9.1.3. *Participating PCCTC Sites*

Participating sites are responsible for performing the following tasks:

- Following the protocol as written, and the guidelines of Good Clinical Practice (GCP).

- Submitting data to the Lead Center. Please follow the submission schedule in section 9.2.1.
- Registering all patients with the Lead Center by submitting patient registration form, and signed informed consent promptly
- Providing sufficient experienced clinical and administrative staff and adequate facilities and equipment to conduct a collaborative trial according to the protocol
- Maintaining regulatory binders on site and providing copies of all required documents to the Lead Center
- Collecting and submitting data according to the schedule specified by the protocol

9.2 Data Entry

Data collected during this study will be entered into a secure database. Staff at the PCCTC coordinating center will be responsible for the initial study configuration and setup in the consortium database and for any future changes.

9.2.1 Case report forms

Case report forms will be generated by the coordinating center for the collection of all study data. Investigators will be responsible for ensuring that the CRFs are kept up-to-date.

The schedule for completion and submission of Case Report Forms and **all** supporting documents to the Lead Coordinating Center is as follows:

Form	Submission Timeline
Eligibility Checklist	Complete prior to registration
Baseline Assessment Form	Within 14 days of registration
On-Treatment Forms (including drug diary)	Within 10 days of course completion
Adverse Event Report Form	Within 14 days of each visit date
Follow-up Form	Within 14 days of visit date
Off Study Form	Within 14 days of being taken off study for any reason

Data should also be submitted within the Johns Hopkins Oncospace Portal.

9.2.2 Source documents

Study personnel will record clinical data in each patient's source documents (ie, the patient's medical record). Source documentation will be made available to support the patient research record. Study monitors will review entries on the CRFs at regular intervals, comparing the content with source documents.

9.2.3 Record retention

The investigator will maintain adequate and accurate records to enable the conduct of the study to be fully documented and the study data to be subsequently verified. After study closure, the investigator will maintain all source documents, study-related documents, and the CRFs. Because the length of time required for retaining records depends upon a number of regulatory and legal factors, documents should

be stored until the investigator is notified that the documents may be destroyed. In this study, records are to be retained and securely stored for a minimum of 3 years after the completion of all study activities.

9.3 Data Management

9.3.1 Lead research program coordinators

A Lead Research Program Coordinator at the Coordinating Center will be assigned to the study. A Lead Research Program Coordinator will manage the study activities at each of the participating sites. The responsibilities of the Lead Research Program Coordinator include project compliance, data collection, data entry, data reporting, regulatory monitoring, problem resolution and prioritization, and coordination of the activities of the protocol team.

9.4 Study Monitoring and Quality Assurance

All clinical trials at SKCCC, Johns Hopkins are required to have Data and Safety Monitoring Plan (DSMP). The Clinical Research Review Committee (CRC) is charged with ensuring that protocols meet the Center's standards for Scientific Merit, Scientific Priority, and Adequate Scientific Progress. The CRC in concurrence with the PI determines the risk level, then reviews and approves the study specific DSMP.

Regularly scheduled registration reports will be generated to monitor patient accruals and the completeness of registration data. Routine data quality reports will be generated to assess missing data and inconsistencies. Accrual rates and the extent and accuracy of evaluations and follow-up will be monitored periodically throughout the study period, and potential problems will be brought to the attention of the principal investigator for discussion and action.

Random-sample data quality and protocol compliance audits will be conducted by the study team at least once a year, more frequently if indicated. Audits by the coordinating center may entail (1) shipping source documents and research records for selected patients from participating sites to the coordinating center for audit, or (2) on-site auditing of selected patient records at participating sites.

All clinical work conducted under this protocol is subject to Good Clinical Practice (GCP) guidelines. This includes inspection of study-related records by the lead site, sponsor, its designee, or health authority representatives at any time.

9.4.1 Data and Safety Monitoring

The SKCCC Compliance Monitoring Program will provide external monitoring for JHU-affiliated sites in accordance with SKCCC DSMP (Version 6.0, 02/21/2019). The SMC Subcommittee will determine the level of patient safety risk and level/frequency of monitoring.

The PI is responsible for internally monitoring the study. Data must be reviewed to assure the validity of data, as well as, the safety of the subjects. The PI will also monitor the progress of the trial, review safety reports, and clinical trial efficacy endpoints and to confirm that the safety outcomes favor continuation of the study

9.5 Clinical Trial Agreement

This trial is being conducted under one or more clinical trial agreements that contain, among other terms, the publication policy, indemnity agreements, and financial arrangements for the study.

9.6 End of Study

This study will end and study database locked when 24 months of follow up is reached from the last patient being enrolled. A final study report will be provided within 3 months of the end of the study.

10. STATISTICAL CONSIDERATIONS

10.1 Study Endpoints

10.1.1 *Analysis of the primary endpoint*

The study is a multi-center, double-blind, placebo controlled, randomized Phase II trial in patients with non-castrate PSA-recurrent prostate cancer after radical prostatectomy. Eligible patients will be randomized in a 1:1 ratio to one of two treatment arms: SRT *plus* placebo (Arm A) or SRT *plus* enzalutamide (Arm B). Randomization will be stratified by center, and surgical margin status (R0 vs R1), PSA prior to salvage treatment (PSA ≥ 0.5 vs < 0.5 ng/mL), and pathologic Gleason score (7 vs 8-10).

The primary objective of the study is to evaluate the efficacy of the two treatment regimens based on freedom-from-PSA-progression (FFPP). FFPP is defined as the time from randomization to the date of PSA progression. A subject who does not have PSA progression at the time of the analysis will be censored at the last date of PSA measurement. In patients who achieve an undetectable PSA value (defined as ≤ 0.1 ng/mL), PSA progression is defined as a detectable PSA value (≥ 0.2 ng/mL) that is confirmed by a second consecutive PSA value obtained ≥ 8 weeks later which is higher (and ≥ 0.4 ng/mL). In patients who do not achieve an undetectable PSA, PSA progression is defined as a 0.2 ng/mL increase from nadir that is confirmed by a second consecutive PSA value obtained ≥ 8 weeks later which is higher.

It is very unlikely deaths in the time frame of this trial will be from prostate cancer. Censoring the subjects that have died at the date of the last PSA measurement before death will be performed (as we will not know if PSA changes in the interval) unless there is clear evidence of death from prostate cancer per the treating physician and/or by autopsy.

FFPP will be summarized using Kaplan-Meier method by treatment arms. FFPP probability will be estimated using the Kaplan-Meier method. FFPP curves will also be displayed graphically. Differences in FFPP between treatment arms will be compared by the log rank test. The Cox proportional hazards regression model will be fitted, and the estimated hazard ratio (Arm B/Arm A) and corresponding 95% CI will be provided. Additionally, Cox regression models will be used to explore the potential influences of the other prognostic factors on the primary FFPP endpoints.

10.1.2 Analysis of secondary endpoints

The first secondary endpoint is time to local recurrence within the radiation field, defined as the time from randomization to the date of local recurrence of disease. Subjects who do not have local recurrence will be censored on the date of their last evaluable tumor assessment for local recurrence. Subjects who start any subsequent anti-cancer therapy without a prior reported local recurrence will be censored at the last evaluable tumor assessment prior to initiation of the subsequent anti-cancer therapy.

The second secondary endpoint is metastasis free survival (MFS), defined as the time from randomization to the date of metastasis or death from any cause up to 90 days following the last response assessment, whichever occurs first. A subject who does not have metastasis and is alive will be censored at the last date of tumor assessment.

Time-to-event endpoints (time to local recurrence and MFS) will be analyzed similarly as described for the primary endpoint (FFPP).

Safety and tolerability will also be evaluated as secondary objectives. For safety analysis, overall safety profile and toleration of Arm A and Arm B will be characterized by type, frequency, severity, timing and relationship of study therapy of adverse events and laboratory abnormalities. Adverse events will be summarized by the frequency of patients experiencing treatment emergent adverse events corresponding to body systems and by worst NCI CTCAE (version 4.0) grade.

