2.2 Secondary Objectives

- Local recurrence within the radiation field (confirmed pathologically)
- Metastasis-free survival (MFS) rates. Metastasis-free survival will be defined as the time from the date of registration to date of evidence of systemic disease on bone scan or cross sectional imaging or death, which occurs first.
- Safety, feasibility, and tolerability as assessed by NCI Common Toxicity Scales (v4.0), quality of life (EPIC survey), and achievement of accrual goals.

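### Section 10.1.2 counts fewer deaths as MFS events than the synopsis and Sections 2.2 and 8.1.2, and MFS and local recurrence are censored at an undefined tumor assessment

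*Combined protocol and SAP*

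**What the plan says.** MFS is defined in four places. Section 8.1.2 gives "radiographic metastasis free survival (rMFS), defined as the time from randomization to the date of metastasis or death from any cause, whichever occurs first". Section 2.2 runs "to date of evidence of systemic disease on bone scan or cross sectional imaging or death, which occurs first", and the synopsis agrees. Only Section 10.1.2 adds a limit: it counts "death from any cause up to 90 days following the last response assessment, whichever occurs first".

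Sections 8.1.2 and 10.1.2 use the same MFS censoring sentence: "A subject who does not have metastasis and is alive will be censored at the last date of tumor assessment". Men without local recurrence "will be censored on the date of their last evaluable tumor assessment for local recurrence". Neither *tumor assessment* nor *response assessment* is defined.

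Section 10.1.2 adds that both time-to-event secondary endpoints "will be analyzed similarly as described for the primary endpoint (FFPP"). For FFPP, Section 10.1.1 says: "Censoring the subjects that have died at the date of the last PSA measurement before death will be performed", with an exception for clear prostate-cancer deaths.

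Post-baseline disease imaging is tied to PSA progression, or done sooner if clinically indicated (Table 1 footnote 6; Section 8.1). Table 1 also marks the scans in the Off-Study column under that footnote. The follow-up visit list in Section 5.2 contains no imaging. On the landmark, Section 8.1.2 says: "We will pay particular attention to the 2-year MFS rate".

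**The concern.** There are two gaps, and they interact.

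The first is the death rule. A metastasis-free man who dies more than 90 days after his last response assessment is an MFS event in three places and not in the fourth. Section 10.1.2 gives him no censoring date either, because its censoring sentence requires him to be alive. The FFPP death rule could be carried over through the word *similarly*, but that sentence may refer only to Kaplan-Meier, log-rank and Cox methods.

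The second is the censoring date. If a tumor assessment is an imaging study, a man with no PSA progression and no indicated or off-study scan is censored at about time zero. Time at risk for MFS then depends on PSA progression, the outcome expected to differ by arm. If a tumor assessment includes clinic visits or PSA, that problem disappears, but the conflict over deaths remains.

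At stake is the 2-year MFS rate. The same data could give several values, and the choice could be made after the results are known.

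**Working it through.** **The plan's own figure.** Only FFPP is sized. Schoenfeld's formula with hazard ratio 0.44, one-sided alpha 0.1 and 90% power gives 4 × (1.2816 + 1.2816)² / (ln 0.44)² = 26.28 / 0.674 = 39 events, as Section 10.4.1 states. Nothing below changes it. No event count or power is given for MFS or local recurrence.

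**Inputs from the document.** 48 men per arm; 2-year FFPP of 60% (A) and 80% (B), exponential; 60 months of accrual plus 21 of follow-up; baseline imaging up to 90 days before Day 1; scans at PSA progression.

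**Assumed, not in the document.** Mortality d of 1% or 2% per year in both arms; metastasis found at 10% of progression scans; uniform entry; no dropout; no other scans.

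**Men without a progression scan at 2 years.** 48 × 0.6 + 48 × 0.8 = 67.2 of 96.

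**At risk at 24 months.** Potential follow-up is uniform from 21 to 81 months, so 57/60 = 0.95 of men can reach month 24.
- Last-contact censoring, ending at PSA progression: 67.2 × 0.99² × 0.95 = 62.6, and 67.2 × 0.98² × 0.95 = 61.3.
- Last-contact censoring, men followed after progression: 28.8 men progress by month 24 and 10% (2.88) have metastasis, so 93.12 × 0.99² × 0.95 = 86.7, or 85.0 at 2%.
- Imaging reading: a man counts only if he progresses after month 24 but before death or cut-off. With λ = −ln(FFPP)/24, μ = −ln(1 − d)/12 and h = λ + μ, the probability is (λ/h)[0.95e^(−24h) − (e^(−24h) − e^(−81h))/(60h)]. At 1% mortality this is 0.232 (A) and 0.164 (B), so 11.1 + 7.9 = 19.0 men. At 2% it is 0.224 and 0.159, so 18.4 men.

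**2-year MFS, simulated (3,000 runs per setting), A / B in %.**

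| Censoring and death rule | 1% mortality | 2% mortality |
|---|---|---|
| Imaging date, 10.1.2 deaths | 90.4 / 91.8 | 89.6 / 91.3 |
| Imaging date, all deaths | 87.0 / 86.5 | 83.3 / 81.8 |
| Visit/PSA date, 10.1.2 deaths | 93.1 / 96.0 | 91.4 / 94.3 |
| Visit/PSA date, all deaths | 92.5 / 95.6 | 90.4 / 93.5 |
| Last contact, ending at PSA progression | 93.3 / 95.9 | 91.2 / 93.9 |
| Last contact, followed after progression | 94.2 / 96.1 | 92.2 / 94.1 |

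**Death rule alone.** On the imaging reading, row 1 minus row 2 is 3.4 and 5.3 points at 1%, and 6.3 and 9.5 at 2%. About 3 to 5 deaths before PSA progression are expected, and about 96% of them would not count under 10.1.2. On the visit/PSA reading, row 3 minus row 4 is 0.6 and 0.4, then 1.0 and 0.8. I carry this as 0.3-1.0 to allow for simulation noise.

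**Censoring date.** Row 5 minus row 1 is 1.6 to 4.1 points. It becomes −0.7 to 1.2 at 5% metastasis, 5.7 to 8.7 at 20%, 2.4 to 4.3 with dropout, 1.9 to 4.0 if the radiotherapy planning CT counts, and −0.3 to 2.0 if 25-50% of non-progressors have one indicated scan.

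**Local recurrence** (no deaths, 10% found at work-up): 90.8 / 92.5 with about 20 men at risk on the imaging reading, against 95.1 / 97.8 with about 64 on last contact.

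**The case against.** The best reply is that the large figures need the extreme reading, in which no non-progressor is ever scanned. Table 1 marks scans at Off-Study, indicated scans are allowed, and Section 8.1 lists tumor markers under outcome assessment, which supports a visit or PSA reading. Mortality and metastasis rates are assumed, and the main illustration ignores the 15% loss to follow-up. All of this stands: the size is conditional. It does not remove the conflict over deaths or supply a definition of the term.

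It is also fair that the censoring date is not a contradiction. Sections 8.1.2 and 10.1.2 agree on it, and 8.1.2 calls the endpoint radiographic. The fault there is a missing definition.

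Three stronger readings are tempting, and the documents do not support them.
- *The arm difference reverses.* In the table, B minus A is negative when all deaths count and living men are censored at the scan date. But a 20,000-run repeat at 1% mortality gave −0.1, not −0.5. Across 5-20% metastasis and 1-2% mortality the mean difference runs from about −2.3 to +1.1 points (−2.7 to +1.8 in a further repeat of 6,000 runs per setting). The standard deviation of the difference between single trials is 11-15 points. No reversal can be claimed.
- *The all-cause death rule of 8.1.2 is at fault.* The distortion comes from pairing all deaths with a stale scan date for living men, not from counting all deaths.
- *The start dates conflict.* The synopsis and 2.2 start MFS at registration, while 8.1.2 and 10.1.2 start it at randomization. Section 4.1.1 makes randomization a step of registration, so this is a wording tidy-up.

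**Conclusion.** The concern holds as a conflict between 10.1.2 and three other definitions, together with an undefined censoring term. It should be fixed. As written, the plan allows more than one 2-year MFS rate from the same data.

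The size depends on what a tumor assessment is. With 1-2% yearly mortality, 10% metastasis at progression scans, no dropout and no other scans, the imaging reading leaves about 18-19 of 96 men at risk at 24 months. Last-contact censoring that ends at PSA progression leaves about 61-63. The death rule alone moves 2-year MFS by about 3-10 points on the imaging reading and 0.3-1.0 point on the visit/PSA reading.

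Confidence is high for the textual conflict only, not for the size of the effect. No claim is made about the direction of the arm difference. MFS and local recurrence are secondary and unpowered, and the FFPP analysis and its 39 events do not change.

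**What to change.** Use one definition in the synopsis and in Sections 2.2, 8.1.2 and 10.1.2: time from randomization to first metastasis on imaging or death from any cause, without the 90-day limit.

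Change the censoring date at the same time, because counting all deaths while censoring living men at an old scan biases MFS downward. Censor a man alive without known metastasis at the last study contact at which he was known to be alive and without known metastasis. Say whether the PSA-only contacts after 24 months (Table 1 footnote 9) qualify. Report censoring at the last imaging date as a sensitivity analysis.

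For local recurrence, censor at the last contact without known local recurrence, and keep the existing rule for subsequent anti-cancer therapy.

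Reconcile Table 1 footnote 8, which keeps men on study until PSA progression, with Section 5.6, which follows them for at least 2 years after treatment or until death. State whether metastasis and vital status are collected after PSA progression. If they are not, end MFS follow-up at PSA progression for both events and censoring, do not count later deaths, and report this as a limitation.

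The cost is wording in four places and no added scans. Collecting data after progression would add some work. There are two downsides. Unscanned men are assumed metastasis-free between contacts. If follow-up ends at PSA progression, the arm difference is somewhat overstated: in the illustration about 2.7-2.8 points against 2.0 with continued follow-up at 10% metastasis, and about 5.1 against 3.8 at 20%.
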